Appendix 4: Budget

Daily Delivery and Supervision of Psychotropic Medication for High-Risk Patients with Severe and Persistent Mental Illness Budget:

EXPENSE	Amount
PERSONNEL: Research Assistant (part-time salary) Subtotal	14,280 14.280
PARTICIPANTS: Participant reimbursement Subtotal	800 800
EQUIPMENT AND SUPPLIES: Computer supplies and maintenance Computer software Duplication of study materials Miscellaneous costs (e.g., database access) Subtotal	800 300 200 1,000 2,300
COMMUNICATION OF RESULTS	2,000
TOTAL DIRECT COSTS	19,380

### **Analyses**

A description of the statistical methods to be employed, including timing of any planned analysis(es). Collected data would be analyzed for significant outcomes comparing before and after (a two year total time frame from pre-index date to post-index date) findings for:

- number of days/visits spent with crisis services (ED & CRC),
- hospital visits/admissions (length of stay) and
- number of incarcerations (as a dependent variable)

These data would be entered into a multivariate analysis of covariance (MANCOVA) model or similar multi-level model with baseline or study time, age and gender as the independent variables. Descriptive statistics would be used to elaborate on patient satisfaction and other variables of interest. Preliminary cost analysis will also be undertaken in anticipation of calculating a net benefit for the daily dispensing services.

The number of subjects planned to be studied. N = 32

The level of significance to be used for any differences p < 0.05

Criteria for the termination of the study. Timeframe of study = approximately one year.

Procedure for accounting for missing, unused, and spurious data. Cleaning data, missing data analyses and manual review of data collected etc.

Procedures for reporting any deviation(s) from the original statistical plan (any deviation(s) from the original statistical plan should be described and justified in protocol and/or in the final report, as appropriate).

All deviations from the statistical plan will be based on the quality of data collected during the study and will be filed as amendments to the protocol with the Ethics Board.

The selection of subjects to be included in the analyses (e.g., evaluable subjects). Participants who are currently part of the Forensics program and who are enrolled in the daily dispensing program and have participated in the program for at least one month will be included in the analyses

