
4 Study Design

The scientific integrity of the study and the credibility of the data from the study depend substantially on the study's design. A description of the study design should include:

4.1 A specific statement of the primary endpoints and the secondary endpoints, if any, to be measured during the study.

The primary endpoints to be measured during the study concern how the daily dispensing program will affect medication compliance and outcomes, hospitalizations, re-incarcerations, and community crisis utilization as

well as participants' perceptions of coercion with regards to taking part in the program and satisfaction with the program.

4.2 A description of the type/design of study to be conducted (e.g., before/after design) and a schematic diagram of study design, procedures and stages of analysis. The *before-and-after design is a reasonable option for this evaluation.*

This study proposes to employ a crossover design where data is collected for 12 months during the study and compared to baseline data retrieved for 12 months for each patient before enrollment into the project. Each patient acts as their own control. All individuals currently in the Forensics program will be asked for their informed consent to participate in the study. The study proposes to collect some personal health identifiers such as participant's personal health identification number (PHIN) and date of birth to be able to link medical records for crisis services, hospitalizations and pharmacy data. Patient names will also be collected to determine the number of contacts with criminal services. All personal identifiers will be stripped from the data for analysis and only aggregate data will be reported and/or published.

4.3 A description of the study's intervention.

The main study intervention is the daily supervision of participants while they self-administer their medications by trained pharmacy staff to ensure compliance. The staff in question will be provided by Leila pharmacy and will in addition provide support so that individuals can transition back into living independently through reminders to attend regularly scheduled medical appointments and counseling on correct use of prescribed medications.

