Leila pharmacy's LEAP program consists of 3 A'S: adherence, accessibility, and autonomy. Regarding adherence, it is common for individuals taking medications to miss doses. The LEAP program dedicates a team to help individuals living in the community to receive their medications daily at their homes. Staff will also spend some time with each individual to ensure the medications are taken appropriately. Missed or refused doses are recorded and reported back to the Leila pharmacy program coordinator.

With respect to accessibility, access to primary care is a growing problem and there are very few solutions available. This is why the Leila pharmacy team includes a nurse practitioner, dietitian, pharmacist and other allied professionals. The nurse practitioner is available to provide bridging care until a permanent family physician is available. Further, a common cause of medication discontinuation is due to the side-effects. For anti-psychotic medications, weight gain, dyslipidemia and increase risk of developing diabetes can all deter an individual from taking their medications regularly and ultimately derail them from their path to recovery. The Leila pharmacy dietitian is available to any of their clients and they can help address nutritional concerns and develop healthy meal plans. Both these services, like many others, are offered at no additional charge.

Regarding autonomy, staff respect each individual's decision and try to offer support whenever they need assistance. This is why the LEAP program is completely voluntary and their goal is be a transitional program. When an individual has made significant progress, the medical responsibilities are shifted back to the client.

5 Selection and Withdrawal of Subjects

5.1 Subject inclusion criteria.

Individuals currently enrolled in the daily dispensing program that are also part of the Forensics program and suffer from severe and persistent mental illnesses, have been repeatedly hospitalized, are repeat users of community crisis services, and/or are in frequent contact with the criminal justice system.

5.2 Subject exclusion criteria.

Individuals who are not currently in the Forensics program – those who are part of the daily dispensing program, but are not Forensic outpatients.

6 Treatment of Subjects

6.1 Procedures for monitoring subject compliance.

Participants will be visited in home on a daily basis.

7 Statistics

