7.1 A description of the statistical methods to be employed, including timing of any planned analysis(ses). Collected data would be analyzed for significant outcomes comparing before and after (a two year total time frame from pre-index date to post-index date) findings for:

- number of days/visits spent with crisis services (ED & CRC),
- hospital visits/admissions (length of stay) and
- number of incarcerations (as a dependent variable)

These data would be entered into a multivariate analysis of covariance (MANCOVA) model or similar multi-level model with baseline or study time, age and gender as the independent variables. Descriptive statistics would be used to elaborate on patient satisfaction and other variables of interest. Preliminary cost analysis will also be undertaken in anticipation of calculating a net benefit for the daily dispensing services.

7.2 The number of subjects planned to be studied.

N = 32

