7.3 The level of significance to be used for any differences

p < 0.05

7.4 Criteria for the termination of the study.

Timeframe of study = approximately one year.

7.5 Procedure for accounting for missing, unused, and spurious data.

Cleaning data, missing data analyses and manual review of data collected etc.

7.6 Procedures for reporting any deviation(s) from the original statistical plan (any deviation(s) from the original statistical plan should be described and justified in protocol and/or in the final report, as appropriate).

All deviations from the statistical plan will be based on the quality of data collected during the study and will be filed as amendments to the protocol with the Ethics Board.

7.7 The selection of subjects to be included in the analyses (e.g., evaluable subjects).

Participants who are currently part of the Forensics program and who are enrolled in the daily dispensing program and have participated in the program for at least one month will be included in the analyses.

8 Ethics

Description of ethical considerations relating to the study.

Ethical considerations relating to the study are that participants may be part of a vulnerable population, and participant characteristics need to be considered as well, such as First Nations individuals. Moreover, the participants are also patients of the principal investigator. To address this issue, the principal investigator will not discuss the study with participants, and will neither encourage nor discourage participation. All study contact will be with a research assistant who is not involved in patient care.

9 Data Handling and Record Keeping

All the data will be maintained in a Redcap database with only authorized individuals having access. All data used for analysis will be stripped of personal identifiers and only aggregate data will be reported.

10 Publication Policy

Publication policy, if not addressed in a separate agreement

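### The model names period but does not declare it a within-patient factor, and it names no patient term. An unpaired MANCOVA is therefore allowed in a study where each patient is their own control.

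*SAP*

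**What the plan says.** Protocol 4.2 sets the design: "Each patient acts as their own control", and "data is collected for 12 months during the study and compared to baseline data retrieved for 12 months for each patient before enrollment".

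The analysis is given in one sentence, identical in Protocol 7.1 and the SAP (Analyses). The data, "comparing before and after (a two year total time frame from pre-index date to post-index date) findings" on crisis service use, hospital use and incarcerations, go into a "multivariate analysis of covariance (MANCOVA) model or similar multi-level model with baseline or study time, age and gender as the independent variables".

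Neither document mentions a patient identifier in the model, a random effect, a repeated-measures declaration, a change score or a covariance structure. The multi-level model is offered as an alternative to MANCOVA, and its levels are not named. The planned number is 32 patients (Protocol 7.2 and SAP). The significance level is 0.05 for any differences (Protocol 7.3 and SAP). No power, effect size, standard deviation or within-patient correlation is given.

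**The concern.** The design is paired, but the sentence that fixes the test does not carry the pairing over. Period varies within a patient, while age and gender vary between patients. Listed together without distinction, they describe a model that can be fitted to 64 rows (32 patients × 2 periods) as if these came from 64 people.

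If a patient's two years are positively correlated, that fit gives wrong standard errors in both directions:

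- For period, they are too large, and a real reduction can be missed.
- For age and gender, they are too small, and chance associations are declared significant too often.

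The choice between a paired and an unpaired model would also be left until the data are in hand, although the two can give different p-values.

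**Working it through.** **Inputs from the documents.** 32 patients, two periods each, alpha 0.05, three outcome groups, and the terms period, age and gender.

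**Assumptions.** Two-sided testing, normal outcomes, and a before/after correlation ρ from 0 to 0.7. For the three-outcome check, the correlation between outcomes is 0.3. The real outcomes are counts and days, so the figures show scale only. The plan states no power figure to reproduce.

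**Period effect, one outcome.** With standard deviation σ in each period:

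- unpaired variance of the before/after difference = 2σ²/32;
- paired variance = 2σ²(1 − ρ)/32;
- ratio of standard errors = 1/√(1 − ρ).

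The effect is set so that the paired t-test (31 df) has 80% power. This is 0.723 SD at ρ = 0 and 0.723·√(1 − ρ) SD otherwise. The unpaired t-test (62 df) is then run on the same simulated data.

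| ρ | Effect (SD) | SE ratio | Unpaired power | Unpaired type I error |
|---|---|---|---|---|
| 0 | 0.723 | 1.00 | 81% | 5.0% |
| 0.1 | 0.686 | 1.05 | 78% | 3.9% |
| 0.2 | 0.647 | 1.12 | 74% | 2.9% |
| 0.3 | 0.605 | 1.20 | 69% | 2.0% |
| 0.5 | 0.511 | 1.41 | 53% | 0.7% |
| 0.7 | 0.396 | 1.83 | 25% | below 0.1% |

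The paired test has 80% power and about 5% type I error in every row.

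**Age and gender effects.** These are constant within a patient, so counting each patient twice understates the variance of their coefficients by a factor of 1 + ρ. For one outcome, the large-sample rejection rate under no effect is 2·[1 − Φ(1.96/√(1 + ρ))]:

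- ρ = 0.3: 1.96/1.140 = 1.72, or 8.6%;
- ρ = 0.5: 1.96/1.225 = 1.60, or 11.0%;
- ρ = 0.7: 1.96/1.304 = 1.50, or 13.3%.

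Simulation of the age test with 32 patients gives 8.8%, 11.2% and 13.8%. With three outcomes tested jointly by an unpaired MANCOVA, a null age or gender effect is rejected in about 5% of runs at ρ = 0, 8%–9% at 0.2, 10%–11% at 0.3, 16%–18% at 0.5 and 21%–22% at 0.7.

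**Does the multi-level option restore the pairing?** In four simulated complete data sets, the period t from a linear model with a patient random intercept, age and gender equalled the paired t to four decimals (for example −3.0816 for both, against −2.4627 unpaired). A patient-level reading of the plan's own alternative therefore solves the problem.

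**The case against.** **The pairing is already there.** Protocol 4.2 states the own-control principle. Period can vary only within a patient. With one program and two periods per patient, the patient is the natural level of a multi-level model. Much of this stands. A reader might infer that the plan is unpaired, or that it abandons its design. The documents do not support that: two paired models fit the sentence as well as the unpaired one does. What remains is that Protocol 4.2 describes the design, while the model sentence sets the test. That sentence offers the multi-level model only as an alternative and names no level.

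**The error is conservative.** This holds for the period test when patients are not selected on prior use. A reader might infer that the gap inflates false claims of a program effect. It does not; it does the opposite. But the error is not conservative throughout, because the age and gender tests become too liberal. No hypothesis on age or gender is stated, so this matters only if their p-values are reported. The 0.05 level is nevertheless set for any differences.

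**The loss is speculative.** Partly so. The correlation is unknown, the loss is small at 0.1–0.2 and absent at zero, and no power target exists to be missed. It cannot be said that the study falls short by a given number of points.

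**Pairing has its own cost here.** This stands. Patients are eligible because they "have been repeatedly hospitalized, are repeat users of community crisis services, and/or are in frequent contact with the criminal justice system" (Protocol 5.1), so use may fall without any program effect. With positive correlation the more sensitive paired test declares such a fall significant more often. One simulation with no program effect illustrates this. It assumed yearly rates of 3, 2 and 1, at least 4 events in the before year, and correlation 0.25–0.37. The paired test rejected in 21.8%–28.6% of runs and the unpaired test in 10.9%–16.3%. This limits what a significant result means. It does not justify wrong standard errors.

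**Conclusion.** The point holds in a limited form and should be fixed. The plan names period but does not declare it within-patient, and it names no patient term. The text therefore permits an analysis that contradicts the own-control design.

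The consequence depends on the before/after correlation, which the documents do not give. At 0.3 to 0.5, a comparison with 80% power when paired drops to 69%–53%, and joint tests of age or gender reject at 10%–18% in place of 5%. At zero correlation there is no loss. These sizes rest on normal outcomes and two-sided testing. The direction of both errors needs only a positive correlation.

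**What to change.** In Protocol 7.1 and the SAP (Analyses), replace the model sentence with one paired analysis. Suggested text:

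> For each outcome, a multi-level model will be fitted with a patient random effect, period (before/after) as a within-patient fixed effect, and age (centred) and gender as patient-level covariates. The period effect will be tested two-sided at 0.05.

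If one overall test is wanted, use Hotelling T² on each patient's after-minus-before differences instead. Describe it as a single joint test, not a test of each outcome, and centre any covariates. Uncentred age would turn the test into one of the change at age zero. In a one-outcome simulation (0.5 SD shift, correlation 0.5, assumed mean age 40 and SD 10) this cut power from 78% to 10%.

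Name one of the two, not both. Three separate tests at 0.05 would carry a family-wise error of up to 1 − 0.95³ = 14.3% if independent, so the per-outcome version should say how that is handled. An offset for observed time belongs only in a log-link count model, not in T² or a linear model.

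Add a sentence that a significant before/after difference will not by itself be reported as a program effect, because patients are selected for high prior use and there is no concurrent control.

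The cost is one sentence in each document, a little analysis work, and a few points of power if the correlation is zero: about 1 point for one outcome, and up to about 4 in a three-outcome count simulation (54% unpaired against 50% paired). No new data or patients are needed.
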